## Data Analysis

### Data Analysis Plan:

The ability of B-lines to identify EVLW will be evaluated by measuring sensitivity and specificity. The table below demonstrates the width of the resulting confidence intervals for sensitivity and specificity (based on exact binomial methods) for a study sample of 60 patients:

If the observed sensitivity & specificity is...	... then the respective 95% confidence intervals will be:
60%	(43, 75)
70%	(53, 83)
80%	(64, 91)
90%	(76, 97)

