testing and is standard-of-care for determination of cardiac output. The only change is that the thermodilution measurements are calculated by the PiCCO™ system using the catheter in the radial artery. Using the transpulmonary thermodilution technique (Figure 2), the amount of extravascular lung water (EVLW) present can be determined. EVLW is fluid within the lungs but outside the vascular compartment. Pulmonary edema is the most common clinical manifestation of EVLW. Normal values of EVLW are suggested to be < 10 mL/kg with increased levels being correlated with worse outcomes including mortality (13) (14). The transpulmonary thermodilution measures EVLW using relationships of intrathoracic thermal volume (ITTV), intrathoracic blood volume (ITBV), pulmonary thermal volume and global end-diastolic volume (GEDV) (Figure 2). Studies have found this transpulmonary thermodilution dilution method to be accurate in the measurement of EVLW (15,16).

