## Subject Information

Target accrual: 60

Inclusion Criteria:

1. All adult patients ( $\geq 18$  years) who are referred for invasive hemodynamic assessment of chronic dyspnea
2. Patients who have the capacity to understand and consent for the research study

Exclusion Criteria:

1. Patients with known interstitial lung disease or pulmonary fibrosis.

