## Endpoints

### Primary:

1. Completion clinically indicated invasive hemodynamic stress testing with adjunct lung ultrasound and pulmonary thermodilution measurements in the 60 patient cohort
2. Data analysis and correlation of LUS measurements with invasive derived hemodynamics
3. Data analysis and correlation of LUS measurements with thermodilution measurements of EVLW

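### The precision table labelled for 60 patients was computed with a denominator of 40, and 60 patients cannot supply 40 for both sensitivity and specificity

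*Combined protocol and SAP*

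**What the plan says.** The same four-row table appears in section H (Statistical Analysis and Power) and under Data Analysis Plan. It is said to show the width of the "resulting confidence intervals for sensitivity and specificity (based on exact binomial methods) for a study sample of 60 patients". The left column is headed "If the observed sensitivity & specificity is" and the right column "then the respective 95% confidence intervals will be", so one set of limits serves both measures:

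- 60%: (43, 75)
- 70%: (53, 83)
- 80%: (64, 91)
- 90%: (76, 97)

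The sample size is the same elsewhere: Subject Information has "Target accrual: 60", and the first primary endpoint refers to "pulmonary thermodilution measurements in the 60 patient cohort". The protocol gives no expected share of patients with raised EVLW, no EVLW-positive or EVLW-negative counts, and no other sample-size, power or precision calculation.

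**The concern.** Two things look wrong. First, the intervals are visibly wider than exact intervals on 60 observations should be, which suggests a different denominator. Second, a single column is offered for two proportions with different denominators. Sensitivity is estimated only among patients who are EVLW-positive by thermodilution, and specificity only among those who are EVLW-negative. If each patient is classified once, the two denominators add to 60.

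This is the only planning calculation in the protocol, and sensitivity and specificity are the only analysis named in the two statistical sections. A reader judging whether 60 patients are enough has nothing else to rely on. If the table is wrong, that reader expects precision on both measures that the design cannot give.

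**Working it through.** **Inputs.** N = 60 (both tables, Subject Information, primary endpoint 1); exact binomial method, two-sided 95% (both tables); observed values 60, 70, 80 and 90% (both tables).

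**Formula.** For x successes in n, the Clopper-Pearson limits are beta quantiles:

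- lower = Beta(0.025; x, n − x + 1)
- upper = Beta(0.975; x + 1, n − x)

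**Step 1: try to reproduce the table at its stated size, then at n = 40.**

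| Observed | Printed | n = 60 (x = 36, 42, 48, 54) | n = 40 (x = 24, 28, 32, 36) |
|---|---|---|---|
| 60% | (43, 75) | (46.5, 72.4) | (43.3, 75.1) |
| 70% | (53, 83) | (56.8, 81.2) | (53.5, 83.4) |
| 80% | (64, 91) | (67.7, 89.2) | (64.3, 90.9) |
| 90% | (76, 97) | (79.5, 96.2) | (76.3, 97.2) |

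At n = 60 no row matches. After rounding to whole percent, seven of the eight limits differ from print by 2 to 4 points and the eighth by 1. At n = 40 all eight limits match; the 70% lower limit is 53.47 before rounding, hence 53.

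**Step 2: rule out other explanations.** Searching every n from 10 to 120 with the exact method, only n = 40 matches all four rows; the next best, n = 39, matches two. Wilson, Wald, Jeffreys and mid-p intervals at n = 60 do not reproduce the table, and none of them matches all four rows at any n from 15 to 100. Exact intervals at n = 60 with alpha varied from 0.001 to 0.099 do not match all four rows either.

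**Step 3: can 40 be the denominator for both measures?** Write n₊ for EVLW-positive patients and n₋ for EVLW-negative, with n₊ + n₋ = 60. Setting n₊ = n₋ = 40 needs 40 + 40 = 80 patients. With 60, the smaller group is at most 60/2 = 30. If n₊ = 40, then n₋ = 60 − 40 = 20, and the reverse.

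**Step 4: what 60 patients deliver.** The prevalence is not stated, so the denominators below are assumptions shown as a range.

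| Observed | Printed | n = 30 (30/30 split, both measures) | n = 20 (smaller group of a 40/20 split) |
|---|---|---|---|
| 60% | (43, 75) | (41, 77) | (36, 81) |
| 70% | (53, 83) | (51, 85) | (46, 88) |
| 80% | (64, 91) | (61, 92) | (56, 94) |
| 90% | (76, 97) | (73, 98) | (68, 99) |

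Widths at an observed 80%:

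- printed: 91 − 64 = 27 points
- n = 30: 92 − 61 = 31
- n = 20: 94 − 56 = 38
- n = 15 (12 of 15): (52, 96), 96 − 52 = 44
- n = 10 (8 of 10): (44, 97), 97 − 44 = 53

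**The case against.** The strongest defence is that the table silently assumes a 40/20 split. It would then be exactly right for the measure with 40 patients. That is true, but the protocol states no such split and does not limit the table to one measure, and the other measure would have n = 20. What stands is a limit on the claim: the table cannot be right for both measures, though it could be right for one. Likewise, a group larger than 40 would have better precision than printed, at the cost of a smaller group on the other side.

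A second defence is that the error is conservative, because intervals at n = 60 are narrower than those printed. That would need all 60 patients in the denominator of each measure, which sensitivity and specificity do not allow. Counting rest and exercise readings separately could change the denominators, but no such analysis is described and the table is stated per sample of patients.

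Three points on consequence are fair. No passage says that 60 was chosen to reach these widths, so calling the table the sample-size justification is an inference, though nothing else could serve as one. The listed primary endpoints concern completion and correlation, and correcting the table leaves the correlation endpoints without any planning figure. At an even split the loss is modest, and the widths of 44 and 53 points depend on few positives, which the protocol neither supports nor excludes. None of this makes the printed figures correct.

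**Conclusion.** The concern holds. The table is mislabelled: its limits are exact intervals for 40 observations, not 60. It is too wide if 60 is taken as the denominator and too narrow for at least one measure under any division of 60 patients by EVLW status. At an observed 80% the understatement of width is about 4 points for both measures at the most even split (31 against 27) and 11 points for the smaller group at 40/20 (38 against 27), with larger gaps if one group is smaller still.

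The mismatch at n = 60 and the match at n = 40 rest on no assumption beyond the method and confidence level that the protocol names. The denominator argument assumes one EVLW classification per patient. The size of the shortfall depends on the unstated EVLW-positive share. Because the error is definite and sits in the only planning calculation, it must be corrected.

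**What to change.** Replace the table in both section H and the Data Analysis Plan. Keep N = 60 and give separate columns for sensitivity (denominator: EVLW-positive patients) and specificity (denominator: EVLW-negative patients) under two or more stated prevalences. For a 30/30 split, both columns take the n = 30 limits in the second table of the working. For a 40/20 split, the group of 20 takes the n = 20 limits, and the group of 40 keeps the limits now printed.

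The new columns need a definition of EVLW-positive. The Methods section says only "Normal values of EVLW are suggested to be < 10 mL/kg", as a normal value and not as the analysis cut-off, so the cut-off, and the B-line threshold that counts as a positive test, should be stated alongside the table. If 40 patients per group was the real intention, the protocol should say so and give a total of at least 80 with its prevalence assumption.

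The cost of restating the table at N = 60 is protocol wording only. No patients or procedures are added; the stated precision becomes less favourable for at least one measure.

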## Endpoints

### Primary:

1. Completion clinically indicated invasive hemodynamic stress testing with adjunct lung ultrasound and pulmonary thermodilution measurements in the 60 patient cohort
2. Data analysis and correlation of LUS measurements with invasive derived hemodynamics
3. Data analysis and correlation of LUS measurements with thermodilution measurements of EVLW

### Secondary:

1. Long-term follow-up at 1-year and 2-year intervals

- a. CVD events (hospitalization, ischemic events, death)
- b. Quality-of-life survey (Kansa city Cardiomyopathy Questionnaire)
